1.3 The need for a pilot trial

A high quality RCT is needed to assess the effectiveness of exercises for patients with AIS. The ultimate aim of this pilot study is, if feasible, to progress to such an RCT which would demonstrate definitively whether or not exercise is clinically and cost effective in AIS management. We estimate that a definitive RCT will require in the region of 400-500 participants (power calculations are in Section 3.7.1). This presents several challenges and is the reason that a pilot study is required before carrying out a full RCT. AIS is a relatively rare condition, and we will require commitment from a substantial proportion of the specialist centres managing AIS in the UK. We need to ensure that there are sufficient numbers of cases who can potentially benefit from the treatment and are willing to participate. The clinicians managing these cases will need to have confidence in the alternative treatments delivered within an RCT to ensure they are willing for patients to be randomised. We also need to maximise the chance that exercise can be effective, not only

by selecting the optimal prescription of exercise, but designing an intervention that encourages compliance. The assumptions underlying the sample size calculation and estimates of recruitment rates also need to be examined.

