2.7 Outcome Measures

2.7.1 Criteria for progression to a randomised controlled trial

The primary outcome of this feasibility trial is to assess if the criteria for progression to a full RCT has been achieved. The progression criteria will be:

1. To demonstrate that the assumptions underlying the sample size, in particular the rates of progression are as anticipated in three centres, that variances are within our estimated range, and that we can achieve or better the recruitment target in these three centres.

We estimate the definitive trial will include between 300-400 participants. This would allow detection of a standardised difference of 0.3, equating to a clinically important 6 degree difference between groups in the Cobb angle (Negrini et al. 2010) (SD of 15 degrees using 80% power, alpha <.05, loss to follow-up of 30%), and also a relative risk reduction of 1.4 in the numbers proceeding to surgery, assuming that 20% of the control group progress to surgery.

2. That we have sufficient numbers of centres, with sufficient numbers of participants in order to finalise the recruitment strategy for a main trial.

Thirty-five NHS Trusts managing AIS in the UK have been identified that could potentially recruit participants in the main trial. There is a wide range of permutations of time, rate of recruitment and number of centres recruiting that could achieve the anticipated sample size but the optimal strategy needs to be finalised. We will also be able to confirm whether patients and their families are willing to accept randomisation as opposed to sourcing exercises themselves, and whether our estimates of the numbers potentially eligible, meeting the various inclusion and exclusion criteria, and finally being randomised are accurate.

3. To have developed an intervention which, based on theoretical models, has sufficient therapeutic dose to limit or reverse progression of curvature and has maximal chance of engaging adherence in adolescents. We must demonstrate that we can deliver a theoretically sufficient dose within current and reasonable levels of NHS resourcing, and that greater than 60% of adolescents will have attended all

supervised sessions and provide evidence that they are undertaking exercises at home.

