6.1 Assessment of progression to a randomised controlled trial

Pilot RCT data will be summarised and reported in accordance with CONSORT guidelines for randomised controlled trials (Schulz et al. 2010). We will report the number of participants approached, the numbers meeting the eligibility criteria, agreeing to randomisation, numbers attending the trial treatment sessions, the overall proportion of people who attend 60% of the sessions and use of the online exercise diary. We will report the parameters needed for sample size estimation, and descriptors of the recruited cohort. Completion of

measures will also be recorded alongside descriptive data. In addition at each site we will also review attendances over the last 2 years to determine the proportions that are likely to progress to surgery as this will be considered in the final calculation of the sample size.

By the end of the study we will be able to determine how many centres we require, how many participants they should be able to recruit, and how long we require them to recruit to the trial for, as well as the variances needed to inform the final sample size calculations. We will have an intervention that is manualised and ready for dissemination in a definitive trial. The overall assessment of feasibility will integrate all of the components of the evaluation. We will specify a protocol for a future trial in accordance with the commissioning brief.

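### The surgery effect in section 2.7.1 (a relative risk reduction of 1.4 from 20%) is impossible as written, and 300-400 participants give 19-45% power if it means a risk ratio of 1/1.4 or a 40% reduction

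*Protocol*

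**What the plan says.** Section 2.7.1 makes the progression criteria the primary outcome of the pilot. Criterion 1 asks the pilot to show that the assumptions behind the main-trial sample size hold. The paragraph beneath it gives those assumptions:

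- Size: "We estimate the definitive trial will include between 300-400 participants".
- Cobb angle: "This would allow detection of a standardised difference of 0.3, equating to a clinically important 6 degree difference between groups in the Cobb angle", with a bracket reading "SD of 15 degrees using 80% power, alpha <.05, loss to follow-up of 30" (per cent).
- Surgery, joined on in the same sentence: "also a relative risk reduction of 1.4 in the numbers proceeding to surgery, assuming that 20% of the control group progress to surgery".

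No exercise-arm surgery rate is given. No power, alpha or loss is given for surgery separately, and neither the sidedness of the test nor the main-trial allocation ratio is stated.

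Two other places bear on this. Section 1.3 puts the same trial at another size: "We estimate that a definitive RCT will require in the region of 400-500 participants". Section 6.1 plans a review of two years of attendances at each site to find the proportion likely to progress to surgery, "as this will be considered in the final calculation of the sample size".

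**The concern.** A relative risk reduction is one minus the risk ratio, so its ceiling is 1, reached when no one in the exercise arm has surgery. A value of 1.4 describes no possible trial result, so the printed statement cannot be checked or used.

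If the number 1.4 is kept and only the label is repaired, the effect becomes a modest one on a 20% event rate, and such effects usually need far more than 300-400 participants. Someone planning the main trial from this paragraph could then believe that the stated size also covers surgery. Depending on what was meant, the required number runs from about 372 to about 1,950, and the text does not say which applies.

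**Working it through.** **Inputs from the protocol.** Section 2.7.1: 300-400 randomised, 20% control surgery rate, 80% power, alpha 0.05, 30% loss (the last three from the Cobb-angle bracket). **Assumed:** two-sided test, 1:1 allocation.

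**Step 1: the claim as printed.** Exercise-arm rate = 0.20 × (1 − 1.4) = −0.08. This is not a probability, so there is no stated figure to reproduce.

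**Step 2: numbers analysed.** 300 × 0.7 = 210, or 105 per arm. 400 × 0.7 = 280, or 140 per arm.

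**Step 3: formulas.** Two independent proportions p1 and p2, with mean p̄ and pooled variance under the null:

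- n per arm = [1.96·√(2p̄(1−p̄)) + 0.8416·√(p1(1−p1) + p2(1−p2))]² / (p1−p2)²
- Power = Φ{[|p1−p2|·√n − 1.96·√(2p̄(1−p̄))] / √(p1(1−p1) + p2(1−p2))}

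**Step 4: a risk ratio of 1/1.4.** p2 = 0.20/1.4 = 0.1429 and p̄ = 0.1714.

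- n = (1.0446 + 0.4473)² / 0.05714² ≈ 682 per arm; 2 × 682 = 1,364 analysed; 1,364/0.7 ≈ 1,949 randomised.
- Power at 105 per arm: Φ[(0.5855 − 1.0446)/0.5315] = Φ(−0.864) = 19.4%.
- Power at 140 per arm: Φ[(0.6761 − 1.0446)/0.5315] = Φ(−0.693) = 24.4%.

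**Step 5: a 40% reduction.** p2 = 0.12 and p̄ = 0.16.

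- n = (1.0162 + 0.4337)² / 0.08² ≈ 329 per arm; 658 analysed; 658/0.7 ≈ 940 randomised.
- Power at 105 per arm: Φ[(0.8198 − 1.0162)/0.5154] = Φ(−0.381) = 35.2%.
- Power at 140 per arm: Φ[(0.9466 − 1.0162)/0.5154] = Φ(−0.135) = 44.6%.

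**Step 6: a reading that fits.** A relative risk of 0.4 gives p2 = 0.08 and p̄ = 0.14.

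- n = (0.9618 + 0.4068)² / 0.12² ≈ 130.1 per arm; 260.1/0.7 ≈ 372 randomised (375 if each arm is rounded up to 131).
- Power is 71.0% at 105 per arm and 82.8% at 140 per arm.

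| Reading | Rates | Power, 300-400 randomised | Randomised for 80% |
|---|---|---|---|
| Risk ratio 1/1.4 | 20% v 14.3% | 19-24% | about 1,950 |
| 40% reduction | 20% v 12% | 35-45% | about 940 |
| Relative risk 0.4 | 20% v 8% | 71-83% | about 372 |

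**Step 7: sensitivity.** For the 40% reduction, a one-sided test with 30% loss gives 47-57%, a two-sided test with no loss 47-59%, and a one-sided test with no loss 60-71%. At 500 randomised, the top of the range in section 1.3, two-sided with 30% loss, power is 29% for 20% v 14.3% and 53% for 20% v 12%. An odds ratio of 1/1.4 does worse: 15-19% at 300-400.

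**Step 8: what the size delivers.** Solving the power formula for p2 at 80% gives 6.9% at 105 per arm and 8.4% at 140 per arm, a relative reduction of about 66% to 58%.

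**The case against.** The strongest reply is that the number is garbled, so no reading of it should be held against the authors. A reader might infer that the stated size fails on every sensible reading. The document does not support that, because it gives no exercise-arm rate, and a relative risk of 0.4 fits the stated size. That reading has to change both the measure and the printed number, so it is not the most literal one, but it cannot be excluded. This part of the reply stands, and it limits the conclusion to the readings computed.

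It is also fair that the 80% power sits in the Cobb-angle bracket. Carrying it to surgery rests on the words that join the two halves of the sentence; no other power is offered.

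A reader might also infer that a decision to proceed would rest on power that the design lacks. The text does not go that far. Criterion 1 tests rates of progression, variances and recruitment; it names no surgery effect. Section 2.8 says that the target effect will be derived later from the systematic review, clinical opinion and pilot data, and section 6.1 plans a final sample size calculation. Nor is the attendance review in section 6.1 an error: it is a sound check on the 20% base rate.

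None of this makes the printed sentence correct. A later recalculation also needs a defined effect to start from.

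**Conclusion.** The surgery claim in section 2.7.1 is wrong as written, whatever assumptions are made about power. Given two-sided 5% alpha, 30% loss, 1:1 allocation and the 80% target carried over from the Cobb angle, 300-400 randomised fall well short for a risk ratio of 1/1.4 (19-24% power) and for a 40% reduction (35-45%). Those effects need about five to six times and about two to three times the stated size (1,950/400 to 1,950/300; 940/400 to 940/300). A 60% reduction would roughly fit.

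This is a planning statement about a future trial whose size is to be recalculated. The pilot's 50 participants rest on estimating variance and recruitment (section 2.8), so its conduct and analysis are untouched. The sentence should be fixed because it stands among the assumptions under progression criterion 1; it is no reason to hold up the pilot.

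**What to change.** Do one of two things in section 2.7.1:

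1. State the intended exercise-arm surgery rate beside the 20%, with the power, alpha (and sidedness) and loss that apply to surgery, and show the number this requires.
2. Replace the claim with what the size delivers, for example: *With 300-400 randomised and 30% loss, 80% power exists only for a fall in surgery from 20% to about 7-8%; power for a 40% relative reduction is 35-45%.*

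In either case, reconcile the 300-400 in section 2.7.1 with the 400-500 in section 1.3, and rerun the figures if the agreed size differs. Keep the two-year attendance review in section 6.1 as the check on the 20% assumption. Whether surgery is a sizing basis or a descriptive outcome in the main trial is a choice for its designers and need not be settled here.

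The cost is one restated sentence, probably with a less favourable figure for surgery, and one cross-check of the total. No pilot participant, procedure or analysis changes.

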Exercise intervention (n=25)

- 6-9 sessions
- home exercise programme over 6 months

Standard Care (n=25)

1 session

On completion of the exercise intervention families will be invited by their physiotherapist to take part in an interview

- Families will be invited until 5-6 families are interviewed
- If they wish to do so then their contact details will be given to the lead qualitative researcher and the family are provided with a Qualitative study PIS.

Telephone call

Lead qualitative researcher contacts the family.

- Further explanation of interview study is provided.
 - The family asks questions.
- Appointment arranged to carry out interviews if the family are happy to do so at least 24 hours later.

Interview appointment

The family meet with the lead qualitative researcher.

- Discuss the interview study PIS.
 - The family ask questions.
- Consent is taken if the family are happy to proceed.
 - Both the child and their parent are interviewed.

The family is contacted by the study team to arrange 6 month follow up appointment.

Follow up research clinic appointment

- Consent to collect data is reconfirmed
- Child undergoes physical assessment
- Child and parent(carer) complete a questionnaire

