2.6.1.2 The exercise intervention

Aims of the exercise intervention

The aims of the exercise intervention are based on the European guidelines for the management of AIS (Negrini et al. 2012, Weiss et al. 2008). Broadly, the aims are to provide a treatment to avoid surgery and or bracing. The specific aims of the exercise intervention are:

- 1) Achieve active auto-correction of spinal deformity
- 2) Address restricted range of movement that may prevent active auto-correction
- 3) Achieve maintenance of the auto-corrected position during movement including integration in activities of daily living
- 4) Improve sensorimotor integration and balance reactions while maintaining the corrected position
- 5) Provide education and support for the participant and family
- 6) Promote strategies to encourage adherence to the exercise programme

Delivery of the exercise intervention

Participants will be asked to carry out the exercise programme primarily as a daily home exercise programme with initial physiotherapy assessment and regular therapy review sessions (up to a maximum of 9 sessions over the 6 months) to provide support, encourage adherence, and allow monitoring and progression of the exercises. Although some clinicians, particularly those following the European schools of thought, advocate prolonged in-patient exercise programmes, recent evidence suggests that such intensive programmes that disrupt normal schooling and socialisation are not necessary (Weiss and Goodall 2009).

Content of the exercise intervention

Each participant will be assessed by their physiotherapist and given an individualised exercise programme based on the presenting spinal deformity. The first step of the exercise programme is to teach the participant to correct their posture (auto-correction to reduce the spinal deformity). Visual, tactile and verbal feedback will facilitate this. Once this has been achieved the participants will be given additional exercises that progressively challenge their ability to maintain the corrected posture by altering position, adding load or resistance, adding movement or distractions and incorporation into activities of daily living.

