2.6.1.3 The control intervention

Participants randomised to the control arm will receive 1-2 sessions (up to one hour) with a physiotherapist which will encompass musculo-skeletal assessment, information and advice regarding their condition and support groups (e.g. SAUK), and, if relevant, information about brace use and care. Participants in both arms will continue to attend for orthopaedic review as per standard practice at their centre. The control intervention will be delivered by the same physiotherapists who deliver the exercise intervention.

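### The adherence criterion in 2.7.1 (over 60% of adolescents attend all sessions) is assessed in 6.1 by a different, never stricter statistic (the share attending 60% of sessions)

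*Protocol*

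**What the plan says.** Section 2.7.1 gives the progression criteria their status: "The primary outcome of this feasibility trial is to assess if the criteria for progression to a full RCT has been achieved". The third criterion requires, besides a theoretically sufficient dose within NHS resourcing, that "greater than 60% of adolescents will have attended all" "supervised sessions and provide evidence that they are undertaking exercises at home". Here 60% is a share of people, and the attendance asked of each person is complete.

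Section 6.1 is headed "Assessment of progression to a randomised controlled trial". Among the quantities to be reported it lists "the overall proportion of people who attend 60% of the sessions and use of the online exercise diary". Here 60% is the attendance asked of each person. No pass mark is put on the share of people, and no arm is named. The section also lists the numbers attending treatment sessions, but not the share who attend all of them.

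The exercise arm is planned at 25 participants (Figure 2 in section 2.5) with 6 to 9 sessions (Figure 2 and Table 1), described in 2.6.1.2 as "up to a maximum of 9 sessions over the 6 months". Control participants "will receive 1-2 sessions (up to one hour) with a physiotherapist" (2.6.1.3). Nothing in the protocol reconciles the two uses of 60%.

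**The concern.** The section that assesses the primary outcome does not name the statistic that the criterion is written in. The one adherence proportion it does name is easier to satisfy. Whoever writes the report then has two figures to hand, both tied to 60%, and no rule saying which one decides. If the choice is made after the attendance data have been seen, the adherence component could be declared met on the 6.1 figure although the 2.7.1 criterion was missed. A definitive trial would then be planned on the belief that adolescents had adhered to supervised exercise to the level the protocol asked for.

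**Working it through.** **Nothing to reproduce.** The 60% is a chosen threshold with no derivation. The check is whether the two statistics can differ, in which direction, and by how much. I read attending 60% as attending at least 60%.

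**Direction.** Let A be the share attending all sessions and B the share attending at least 60% of them, in the same participants. Everyone counted in A is counted in B, so B ≥ A whatever the attendance pattern. The home-exercise condition in 2.7.1 can only widen the gap.

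**A simple case.** Of 25 participants, 10 attend every session and another 10 attend at least 60% but not all. Then A = 10/25 = 40%, below the mark. B = 20/25 = 80%, above 60%.

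**Inputs for the size.**
- n = 25 in the exercise arm (Figure 2).
- k = 6 to 9 sessions (Figure 2, Table 1).
- Pass mark above 60%: 15/25 is exactly 60%, so at least 16 are needed.
- Attendance per session p: not in the protocol, so assumed.

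**Independent sessions.** A = p^k. B = P(X ≥ m), with X binomial(k, p) and m = 0.6k rounded up, so m = 4, 5, 5, 6 for k = 6, 7, 8, 9. The chance of passing is P(Y ≥ 16), with Y binomial(25, A) or binomial(25, B). In the last column the 60% mark is carried over to B, which 6.1 itself does not do.

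| p | A, k = 6 to k = 9 | B, range over k = 6 to 9 | P(pass) on A, k = 6 to k = 9 | P(pass) on B |
|---|---|---|---|---|
| 0.80 | 26% to 13% | 85-94% | about 0 | 0.998 or more |
| 0.90 | 53% to 39% | 97-99% | 0.19 to 0.01 | about 1 |
| 0.95 | 74% to 63% | over 99% | 0.90 to 0.55 | about 1 |

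For example, 0.90^6 = 0.531 and 0.90^9 = 0.387. For A to reach 60%, p must be 0.60^(1/6) = 0.918 with 6 sessions, or 0.60^(1/9) = 0.945 with 9.

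**Correlated sessions.** Some children attend reliably and others drop out, so independence is doubtful. Take a beta-binomial with mean 0.90 and an assumed within-child correlation of 0.3. The beta parameters are 0.90 × (0.7/0.3) = 2.1 and 0.10 × (0.7/0.3) = 0.233.
- k = 6: A = 71%, B = 92%.
- k = 9: A = 65%, B = 91%.

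B is 90% at k = 7 and 93% at k = 8. The gap is now 21 to 26 points at k = 6 and k = 9, and A itself exceeds 60%.

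**Precision at the pass mark.** The exact (Clopper-Pearson) 95% interval for 16/25 = 64% is 43% to 82%.

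**The case against.** The strongest reply is that there is only one threshold. Section 2.7.1 sets a rule; 6.1 lists quantities to report and attaches no pass mark. That is correct: the two sections disagree on a decision only if the 6.1 figure replaces the criterion or borrows its 60% mark. What remains is that the assessment section names a different proportion from the one the criterion needs. The needed share could probably be derived from the session numbers that 6.1 also reports and the treatment logs in 2.12, but no text says that it will be.

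A reader might infer more than the protocol supports, in four ways.

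- **That the same data could stop or start the definitive trial.** Attendance cannot start it alone. Criterion 3 has further parts, criteria 1 and 2 are separate, and 6.1 says the feasibility assessment integrates all components.
- **That control attendance would be counted.** The word overall in 6.1 leaves this open, but criterion 3 concerns the exercise intervention, and 6.1 pairs the phrase with the exercise diary. It is a possible reading, not a stated plan.
- **That the session counts contradict each other.** A maximum of 9 is the top of 6 to 9. In an individualised programme, all can reasonably mean all the sessions arranged for that child.
- **That criterion 3 would fail at 90% attendance.** It would probably fail if sessions were independent, but the correlated model puts the expected share above 60%.

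**Conclusion.** The point holds as a mismatch between a stated component of the primary outcome and the statistic named to assess it. That B is never below A rests on no attendance assumption, only on using the same participants and reading 60% as at least 60%. The size does rest on assumptions. At 90% attendance the comparison is 39-53% against 97-99% if sessions are independent, and 65-71% against about 91-92% (at 9 and 6 sessions) with a within-child correlation of 0.3. At 95% independent attendance it is 63-74% against over 99%, and both figures would often clear 60%. Opposite conclusions on adherence are therefore possible but not established. The consequence is confined to the adherence component and does not by itself decide progression. It still merits correction, because it concerns the declared primary outcome and leaves a choice open until after the data are seen.

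**What to change.** Before attendance data are reviewed, reconcile 2.7.1 and 6.1 so that both give:

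- one definition of an adherent participant and one pass mark on the share of participants;
- the exercise arm only, with everyone randomised to it in the denominator;
- each child's attendance counted against the sessions arranged for that child;
- the resulting proportion with an exact 95% confidence interval.

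If the other statistic is also reported, label it descriptive. Which definition to keep is the sponsor's decision. The number of sessions need not and should not change for this purpose.

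The cost is wording in two sections. The logs already record sessions attended (2.12). The number arranged for each child must be recorded too, if the log does not already hold it.
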